8.0 Costs to Participants

- There are no costs to participants. The study will take approximately 1 hour initially (10 minutes consent, 15 minutes pre-test, 30 minutes education tool, 5 minutes post test). The one month follow survey will take approximately 30 minutes.
- For medical staff participants, surveys will take less than 5 minutes; post-intervention interviews will take approximately 30 minutes.

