13.0 Statistical Analysis

- **General analyses:** After screening for potential differences across sites on the key outcome variables, all data will be graphed and tabulated by group (i.e., **mychoice** vs. control) for review of distributional properties and anomalous values prior to the main analyses. Continuous and normally distributed variables will be summarized with means and standard deviations. All parameter estimates will be bound by 95% confidence intervals. Tests of significance will be based on adjustments for alpha to protect family-wise error rates at 5% using the method of Benjamini and Hochberg [40]. Data will be analyzed using an intent-to-treat (ITT) approach where subjects are analyzed according to their treatment assignment at randomization, regardless of level of participation or engagement. Because an ITT analysis is planned, we will evaluate models suitable for non-ignorable (missing not at random) data within a sensitivity analysis framework in order to determine the extent to which analysis conclusions depend on the assumptions being made about unobserved values. We will perform model-based analyses with direct maximum likelihood methods, including those for data missing not at random (MNAR) if necessary. We will screen for violations of assumptions for all statistical tests involved. All analyses for specific aims will be conducted using SAS 9.4.

- **H1 Analysis:** The principle endpoint will be 1-month follow-up, i.e., one month after completion of either the **mychoice** or control education. We will conduct a mixed-effect regression models for each repeatedly measured continuous outcome (i.e., self-efficacy and decisional conflict at post intervention and 1-month follow-up) on a dummy grouping variable (**mychoice**, as compared to Control), adjusting for baseline level of this outcome and covariates discovered to be unbalanced between the two groups, and moderators of interest. In these models, we will treat time as a categorical variable and examine the fixed effects for time, intervention group, and their interactions. We will specify the covariance structure within patients using an unstructured model to account for the in-patient correlation over time.

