In addition, the dichotomous race (White vs. non-White) variable and the non-White-Treatment interaction will be entered in each regression model as predictors, to understand possible different effects of **mychoice** for non-White vs. White participants. A significant, positive regression coefficient of the non-White Treatment interaction indicates non-white participants' benefits more from the treatment than their White counterparts.

- **Power:** Power analyses were performed using G*Power 3.1, with 2-sided tests and an adjusted alpha level of .025 (= .05/2) for multiple group comparisons. We performed power analyses for comparisons on primary and secondary outcomes for Aim 1. Effect size (mean difference between groups divided by the pooled standard deviation) is a common measure for assessing the magnitude of a treatment effect on continuous outcomes. The number of participants needed for Aim 1 is selected to sufficiently power the detection of a difference between groups on the outcomes adjusting for covariates and moderators at 1-month follow-up.

To detect a moderate treatment effect size of 0.47 SD on either the self-efficacy and decisional conflict scales, our trial would need 88 patients per group, presuming alpha = .025 and beta = .20 (power = 80%). Of note, this effect size is comparable to prior studies (please cite some papers). Including a 20% adjustment for dropout and loss of degrees of freedom when adjusting for possible additional confounding variables, a total of 220 patients are needed. By using mixed-effects repeated measures regression analysis, our power is likely to be even higher. Therefore our estimated power provides a conservative lower-bound of the likely actual power of our sample size. Also, we will need an additional 50 patients to do exploratory analysis on potential differences in effect by recruitment type, bringing the total needed to 270.

- **H2 Analysis:** Descriptive statistics will be employed for the analysis of the quantitative feasibility and acceptability data. All qualitative data collected through the meeting notes and debriefing interviews will analyzed the Krueger method of analyzing narrative data will be used; familiarization, identifying a thematic framework indexing, charting, mapping and interpretation [80]. Recordings will be listened to and transcriptions read to become familiar with what participants said. A

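### The H1 mixed model names no baseline-by-time term, so one baseline slope serves both the same-session post-test and the principal 1-month endpoint, at a possible cost in precision

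*Combined protocol and SAP*

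**What the plan says.** Section 13.0, H1 Analysis, fits one mixed model per primary outcome to two repeated values: "self-efficacy and decisional conflict at post intervention and 1-month follow-up". On timing it states "The principle endpoint will be 1-month follow-up". The model is specified as "adjusting for baseline level of this outcome and covariates discovered to be unbalanced between the two groups, and moderators of interest", and then, with time taken as categorical, it will "examine the fixed effects for time, intervention group, and their interactions". For the residuals, "We will specify the covariance structure within patients using an unstructured model".

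The only interactions named there refer back to time and group. The following paragraph adds a race-by-treatment term. Baseline is not crossed with time anywhere.

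Section 8.0 gives the course of the first session: "10 minutes consent, 15 minutes pre-test, 30 minutes education tool, 5 minutes post test". Table 1 in section 4.0 lists the self-efficacy and decisional conflict scales at pre-test, post-test and 1 month.

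The Power paragraph of section 13.0 sizes the trial on an unadjusted two-group comparison and then adds: "By using mixed-effects repeated measures regression analysis, our power is likely to be even higher". It presents its figure as a cautious floor on the true power, and gives no correlation between time points.

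**The concern.** A programmer who fits the model as written will estimate one baseline coefficient for two quite different measurements. One repeats the same scale in the same session, about half an hour later. The other is taken after a month, in which other influences on the patient have had time to act. The first would be expected to follow baseline more closely than the second.

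With an unstructured covariance, maximum likelihood gives more weight to the time point with the smaller residual variance, here the post-test. The shared slope is then too steep for the 1-month value, and the 1-month contrast is over-adjusted. At stake is part of the precision that baseline adjustment should bring to the principal endpoint, and with it part of the extra power that the Power paragraph expects from the mixed model.

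**Working it through.** **1. The plan's own figures.** Inputs from section 13.0, Power: effect 0.47 SD, two-sided alpha .025, power 80%. The normal approximation gives 87 per group. The exact two-sample t calculation (noncentrality 0.47 × √(88/2) = 3.118, 174 df) gives 88 per group with power 80.3%. Then 176 / 0.80 = 220, and 220 + 50 = 270. All three figures reproduce. None of them uses a baseline correlation.

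**2. Assumptions.** The documents give no correlations, so these are assumed: r1 = baseline with post-test, r2 = baseline with 1 month, r12 = post-test with 1 month. SDs are 1 at every time point, data are complete, and time-by-group is in the model.

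**3. Formulas.** With a separate slope at each time, the residual covariance has s11 = 1 − r1², s22 = 1 − r2², s12 = r12 − r1·r2. The maximum-likelihood common slope is

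b = w·r1 + (1 − w)·r2, with w = (s22 − s12) / (s11 + s22 − 2·s12).

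The variance of the 1-month contrast is proportional to

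- own slope at 1 month: 1 − r2²
- common slope: (1 − r2²) + (b − r2)²
- no baseline adjustment: 1

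The common slope is worse than no adjustment only if (b − r2)² > r2², that is, if b > 2·r2.

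**4. One case in full (.8/.5/.6).** s11 = .36, s22 = .75, s12 = .6 − .4 = .20. w = .55 / .71 = .775. b = .775 × .8 + .225 × .5 = .732. Common-slope variance = .75 + .232² = .804. Ratio to .75 = 1.072, so the standard error is √1.072 = 1.035 times as large.

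**5. Results.** Power is from the same t calculation at 88 per group and alpha .025, with effect 0.47 / √variance.

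| r1 / r2 / r12 | b | 2·r2 | Variance, common vs own slope | 1-month SE | Power, common vs own slope |
|---|---|---|---|---|---|
| .6 / .6 / .6 | .600 | 1.2 | .640 vs .640 | +0% | 94.8% vs 94.8% |
| .7 / .5 / .6 | .632 | 1.0 | .767 vs .750 | +1.1% | 90.2% vs 90.9% |
| .8 / .5 / .6 | .732 | 1.0 | .804 vs .750 | +3.5% | 88.7% vs 90.9% |
| .85 / .4 / .5 | .784 | 0.8 | .987 vs .840 | +8.4% | 80.9% vs 87.2% |
| .8 / .3 / .3 | .670 | 0.6 | 1.047 vs .910 | +7.2% | 78.3% vs 84.2% |

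Unadjusted power is 80.3% throughout. Only the last row passes the break-even point b > 2·r2.

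**6. Share of the baseline gain lost,** (b − r2)² / r2²: .0173/.25 = 7% at .7/.5/.6; .0540/.25 = 22% at .8/.5/.6; .1472/.16 = 92% at .85/.4/.5.

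**7. Check with dropout.** Trials of 220 patients were simulated with 20% of 1-month values missing completely at random, 2,000 runs per scenario. The variance inflation was 0.7% at .7/.6/.6, 2.1% at .7/.5/.5, 8.8% at .8/.5/.5, 11.2% at .8/.4/.4 and 16.7% at .9/.5/.5. The mean estimate stayed at 0.47, and the model variance tracked the empirical variance.

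**The case against.** The strongest reply is that nothing here is invalid. A single baseline coefficient is a common specification, and under randomisation the 1-month contrast stays centred on the true effect, as the simulation showed. A reader might infer a biased comparison, but this is not supported. Over-correction of a chance baseline difference is the same loss of precision described another way, not a second harm.

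A reader might also infer that the trial is underpowered. The documents do not support that either. The 88 per group comes from an unadjusted comparison and relies on no gain from baseline; the extra power is mentioned only as an unquantified bonus. At the plan's 0.47 SD, power stays above 80.3% in every case in the table except the steepest drop. The planned 270 leave 270 × 0.80 / 2 = 108 per group after 20% dropout. With 108, the figures are 95.3% vs 95.8%, 94.4% vs 95.8% and 88.8% vs 93.4% for .7/.5/.6, .8/.5/.6 and .85/.4/.5.

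Finally, the plan neither imposes a common slope as a restriction nor rules out the interaction, and it promises a general check of model assumptions. The correlations are assumed, and equal slopes would mean no loss.

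All of this stands, and it limits the point to efficiency. It does not supply the missing term: the general promise to check assumptions does not mention baseline-by-time, and nothing else in the plan does.

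**Conclusion.** The point holds as an optional, free improvement. As written, the model has one baseline slope for two time points at which baseline is likely to predict differently. That ordering is a judgement from the timing in section 8.0; the documents report no data on it, and patients who take part at home may space the tests differently.

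Under the assumed correlations, the loss at 1 month runs from nil to 8.4% of the standard error, and from nil to about 6 percentage points of power at 0.47 SD and 88 per group. The Power paragraph's claim of a cautious floor fails on this account only when the correlation with baseline drops very steeply, as at .8/.3/.3 (78.3% against 80.3% unadjusted). The absence of bias was checked only with 1-month values missing completely at random.

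**What to change.** In section 13.0, H1 Analysis, add the baseline-by-time interaction to the prespecified fixed effects for both primary outcomes, and state that the treatment contrast at 1 month is taken from that model. The 1-month contrast then uses its own baseline slope.

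The cost is one model term and one degree of freedom per outcome, with no extra patients or data; 88 per group, 220 and 270 stay as they are. If the slopes turn out equal, almost nothing is lost. Naming the term in advance also avoids a later choice between two models that could give different 1-month p-values.

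### The only race rule asks whether non-White patients gain more than White patients; no contrast is named for the H1 and H2 claim that mychoice beats control within non-White patients, and the rule's sign does not fit decisional conflict

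*Combined protocol and SAP*

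**What the plan says.** Section 2.0 holds two different race questions. The primary objective asks whether the effects are larger in minority patients. H1 (self-efficacy) and H2 (decisional conflict) each claim superiority over the non-tailored aid in all patients and also in the non-White subsample. Neither hypothesis gives a time point.

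Section 13.0, H1 Analysis, supplies one: "The principle endpoint will be 1-month follow-up". The mixed model for each outcome takes "self-efficacy and decisional conflict at post intervention and 1-month follow-up" as its repeated measures, adjusts for baseline, and will "examine the fixed effects for time, intervention group, and their interactions". The race paragraph then adds that "the dichotomous race (White vs. non-White) variable and the non-White-Treatment interaction will be entered in each regression model as predictors", the purpose being "to understand possible different effects of" the tool by race. Its one decision rule is that a significant positive coefficient means non-White patients show "benefits more from the treatment than their White counterparts".

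Other places come close without filling the gap. Section 4.0 expects about 20% non-White patients and foresees subgroup analyses without defining them. The H1 Analysis mentions moderators without listing contrasts. The paragraph headed H2 Analysis deals with feasibility and qualitative data, so it adds nothing on decisional conflict by race.

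**The concern.** A difference between two subgroup effects is not the effect in one of them. The written rule tests the first, and half of each hypothesis asserts the second. Followed literally, a null interaction could be reported as failure of the subgroup hypothesis when the tool helps everyone equally, and a positive one as proof of benefit when non-White patients gained nothing.

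Two further consequences come from the same paragraph. The rule applies to every outcome model with a positive sign, yet H2 expects decisional conflict to go down. And because the race terms enter the same models that carry the primary comparison, the treatment coefficients change meaning: under ordinary dummy coding they describe White patients.

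A secondary matter is time. The post-test is part of the initial session ("15 minutes pre-test, 30 minutes education tool, 5 minutes post test", section 8.0), while the principal endpoint is a month later. Only a two-way race term is named, so on the natural reading the race difference is taken to be the same at both surveys, and the plan does not say so.

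**Working it through.** **1. The plan's own sizing.** Section 13.0, Power, gives 0.47 SD, two-sided alpha .025, 80% power and "our trial would need 88 patients per group". A two-sample t-test calculation gives 87.3, so 88, with power 0.803. Then 2 × 88 / 0.8 = 220, and 220 + 50 = 270. These figures reproduce. The extra 50 are for recruitment type, not race.

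**2. What the race coefficient measures.** Write D_W and D_N for the mychoice-minus-control effects in White and non-White patients. The coefficient is D_N − D_W; the H1/H2 subgroup claim concerns D_N. Illustrative effects, higher score better:

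| D_W | D_N | Coefficient | Subgroup claim | Rule |
|---|---|---|---|---|
| 0.47 | 0.47 | 0 | true | fires only by chance: 1.25% at two-sided .025, 2.5% at .05 |
| −0.50 | 0 | +0.50 | false | favours a positive reading |
| −0.30 | 0.20 | +0.50 | true | same coefficient as the row above |

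**3. Sign.** For decisional conflict benefit is negative. With assumed effects of −0.40 (White) and −0.75 (non-White), non-White patients benefit more and the coefficient is −0.75 − (−0.40) = −0.35. Swap the two and it is +0.35, which the rule would read as greater non-White benefit. The rule works only if the scale is reversed, which the plan does not mention.

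**4. The all-patient effect.** With terms for group, time, group × time, race and race × group, and White as reference, group + group × time at 1 month equals D_W. Take constant effects of 0.40 (White) and 0.75 (non-White) and the plan's 20% share:
- from the treatment coefficients: 0.40
- weighted by race mix: 0.8 × 0.40 + 0.2 × 0.75 = 0.47
- equal race weights: (0.40 + 0.75) / 2 = 0.575

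The plan does not say which of these is the primary estimate.

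**5. The two-way term over two surveys.** Assumptions: equal SDs at both surveys, within-patient correlation 0.3 to 0.7, 135 per arm, expected generalised least squares estimates. With complete data the model averages the race difference over the two surveys, so it misses the 1-month difference by half of any change. Since D_N is the all-patient effect plus 0.8 × the race difference, the bias in D_N at 1 month is 0.8 × 0.5 = 0.40 × (race difference at post-test minus that at 1 month). If 20% miss the 1-month survey the factor is 0.46 to 0.47.
- Mild change (White 0.40 at both; non-White 0.57, then 0.47): 0.51 to 0.52 against 0.47, 95% CI coverage about 95%.
- Middle (White 0.47 at both; non-White 0.705, then 0.47): 0.56 to 0.58 against 0.47, coverage about 93%.
- Extreme (White 0; non-White 0.47, then 0; complete data): 0.19 against 0, coverage 87 to 89%.

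The averaged term has the lower mean squared error unless the race difference shifts by more than about 0.24 to 0.36 SD (complete data) or 0.26 to 0.39 SD (20% missing).

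**6. What the missing contrast can deliver.** Non-White patients per arm, with the whole 20% allowance counted as dropout: 0.2 × 220 / 2 × 0.8 = 17.6 and 0.2 × 270 / 2 × 0.8 = 21.6, so about 18 to 22. At two-sided .025:
- power for 0.47 SD without baseline adjustment: 19 to 23%
- with an assumed baseline correlation of 0.5, the effect becomes 0.47 / √(1 − 0.25) = 0.543 residual SD: 25 to 31%
- with 0.7: 37 to 45%
- 27 per arm (270 patients, no dropout), unadjusted: 29%
- effect detectable with 80% power, unadjusted: 1.07 to 0.96 SD

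**The case against.** The interaction is the right tool for the primary objective, which asks about an enhanced effect. That it is 0 when the races gain equally is true by definition and is no fault of the coefficient. This stands: the gap is a missing second contrast, not a wrong first one.

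A reader might go further and infer that averaging over the two surveys is an error that spoils the 1-month race result. The documents do not support that. The averaging is inferred from the terms named; nothing rules out race-by-time terms, and the Power paragraph speaks of moderators at 1 month. Coverage stays at 93 to 95% in the mild and middle cases, and the averaged term is the more efficient choice unless the race difference shifts by roughly half or more of the design effect. It is a defensible choice whose assumption should be written down.

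A non-White 1-month effect could be assembled from the planned model. True, but the plan neither names it nor states the assumption on which it would rest.

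The precision figures can fairly be called pessimistic. The plan adjusts for baseline, its 20% allowance also covers lost degrees of freedom, and the 20% non-White share is a monitored target with a recruitment change if it is missed. Even at a baseline correlation of 0.7, power stays below one half.

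**Conclusion.** The concern holds as a mismatch between hypothesis and analysis, and that part needs no assumed numbers: as written, the plan cannot answer the subgroup half of H1 or H2, and its sign rule misreads one of the two primary outcomes unless that scale is reversed. It should be fixed before analysis.

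It would be too strong to say that the all-patient comparison is invalid, and equally too strong to say that it is untouched. It is sound if taken from a model without the race interaction or from a contrast weighted by race mix; read off the dummy-coded treatment terms it is the White effect. The 0.40 against 0.47 illustration rests on assumed effects and the 20% share.

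The constant-over-time assumption is a trade-off to be stated, not a defect. The power range of 19 to 23%, or 25 to 31% at an assumed baseline correlation of 0.5, means that the non-White effect can be estimated but not confirmed at this size.

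**What to change.** - Take the primary all-patient 1-month effect from the model without the race × treatment term, or from a stated contrast weighted by the observed race mix.
- For each outcome, add a separate subgroup model. Report at 1 month, with 95% CIs, the mychoice-minus-control effect in non-White patients, the effect in White patients and their difference. Include race × time and race × group × time so that these are specific to 1 month; if the two-way term is kept instead, state that the race difference is assumed constant over time.
- State the direction of benefit for each outcome: higher self-efficacy, lower decisional conflict.
- Label the non-White effect as an estimate outside the confirmatory multiplicity family, and say so in H1 and H2.

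The cost is SAP wording and one extra model per outcome on data already collected. For correlations of 0.7 down to 0.3, the 1-month interaction's standard error is 8 to 24% larger than that of the averaged term with complete data, and 13 to 33% larger if 20% miss the 1-month survey.

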2.0 Objectives

- The **primary objective** of the study is to assess the effectiveness of the **mychoice** mHealth tool on perceived patient self-efficacy and decisional conflict, and whether these results are enhanced in minority patients.
- The **secondary objective** of the study is to describe the acceptability and feasibility of implementing **mychoice** in oncology services at three leading cancer centers in Philadelphia.
- **Purpose of the study:** **mychoice** was conceptualized and developed with a Fox Chase-Temple NODAL grant, using extensive formative research, including the use of commercial marketing techniques (perceptual mapping and vector modeling) and

patient engagement, and customized to address the significant barriers for African American patients to consider clinical trials. The tool went through user testing and received excellent reviews, and now is ready for an efficacy test. This study represents the next step in personalized clinical trial education research. It completes the **mychoice** communication tool to make it multi-cultural and thus appropriate for all patients, and tests its effectiveness with diverse cancer patients to improve knowledge and preparation to discuss clinical trials within real world settings. We will also explore organizational factors that impact implementation of a technology-based intervention, an innovative aspect that will provide critical understanding on feasibility to ensure scalability in a large medical setting. Results could inform how a tool like **mychoice** could be implemented in a cancer center and enhance communication about clinical trials between patients and doctors.

- **Specific Aims:**

- **AIM 1:** Test the perceived usefulness and effectiveness of **mychoice** to increase patients' self-efficacy and decrease decisional conflict.
 - **AIM 2:** Describe the acceptability and feasibility of implementing **mychoice** in oncology services at three leading cancer centers in Philadelphia by identifying provider and organizational factors influencing its integration in the clinical space.
- The following **hypotheses** are proposed for Specific Aim 1:
 - **H1:** Compared to a non-tailored education aid, **mychoice** will improve self-efficacy in making a decision about participating in clinical trials for all patients as well as a subsample of underrepresented patients (non-white).

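### Race x treatment is entered in every primary model and no all-patient contrast is named, so the usual group tests do not address the all-patient part of H1 and H2

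*Combined protocol and SAP*

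**What the plan says.** Section 2.0 states two hypotheses, each with two populations. H1 concerns self-efficacy in decisions about "clinical trials for all patients as well as a subsample of underrepresented patients (non-white". H2 makes the same pair of claims for decisional conflict.

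Both outcomes are analysed under the H1 Analysis heading in section 13.0; the H2 Analysis heading there covers the descriptive Aim 2 work. Each outcome is regressed "on a dummy grouping variable" (mychoice against control), with categorical time, group x time, the baseline value, unbalanced covariates and moderators of interest. One month is the principal time point.

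The next paragraph says that the dichotomous race "variable and the non-White-Treatment interaction will be entered in each regression model as predictors", in order to see whether the effect differs by race. No model without the interaction is described. No race coding, centring, reference time or weighting is given for an all-patient test.

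The Power paragraph works with an effect of 0.47 SD and an "adjusted alpha level of .025 (= .05/2) for multiple group comparisons". It arrives at 88 per group, 220 after a 20% allowance, and 270 with 50 more for an exploratory question. It concludes: "Therefore our estimated power provides a conservative lower-bound of the likely actual power of our sample size". Section 4.0 expects about 20% of participants to be non-white and allows recruitment to be refocused if that is not reached.

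**The concern.** Once race x treatment is in a model, there is no longer one treatment effect to read off. With group and race both coded 0/1 and White as zero, the group coefficient is the effect in White patients. Because group x time is also present, it is that effect only at the reference time, which need not be 1 month. If group and race are SAS CLASS variables and the Type 3 group test is used instead, the two race-specific effects are averaged 50:50 against an expected mix of 80:20.

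These are the two results an analyst would most naturally report from the model as written, and neither is the all-patient difference at 1 month. If non-White patients benefit more, as the objectives hope, the first understates the all-patient effect and the second overstates it. Both are also less precise than the comparison on which the sample size rests. Leaving the choice open would allow the primary test to be settled after the results are known.

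**Working it through.** **Inputs from the documents.** Effect 0.47 SD, two-sided alpha 0.025, 80% power, 1:1 allocation, 88 per group (176 evaluable), 20% inflation, total 270, about 20% non-White. **Assumptions.** SD 1, the same 0.47 effect in both races for the power figures, race balanced across arms, a single comparison at 1 month, and a baseline correlation rho that is not given and is varied below.

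**1. The plan's own figure.** For two equal groups the noncentral t calculation gives power 0.798 at 87 per group and 0.803 at 88. Then 176 / 0.8 = 220. Both figures reproduce, as a plain two-group comparison with no moderator.

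**2. What each quantity estimates.** Let q be the non-White share and d the interaction (non-White effect minus White effect).
- All-patient effect = White effect + q x d.
- 0/1 group coefficient = White effect, so it misses by -q x d.
- Equal-weight average = White effect + 0.5 x d, so it misses by (0.5 - q) x d.

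As an illustration only, take 0.40 in White and 0.75 in non-White patients, so d = 0.35. The all-patient effect is 0.8 x 0.40 + 0.2 x 0.75 = 0.47. The group coefficient is 0.40, and the equal-weight average is (0.40 + 0.75)/2 = 0.575, which is 0.105 too high. A simulation of 200,000 records with these values gave a group coefficient of 0.402 with 0/1 race and 0.473 with race centred at 0.2.

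**3. Precision.** The all-patient difference has variance 4/N. Relative to that, with q = 0.2:
- White only: 1/0.8 = 1.25.
- Equal weights: 0.25 x (1/0.8 + 1/0.2) = 1.5625.
- Race-share weights on the interaction model: 0.8²/0.8 + 0.2²/0.2 = 1.00.

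**4. Power at 0.47 SD.** Noncentral t, with each variance multiplied by 1 - rho² for baseline adjustment. The 216 is 270 x 0.8.

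| Evaluable | rho | White only | Equal weights | Share-weighted |
|---|---|---|---|---|
| 176 | 0 | 0.701 | 0.593 | 0.803 |
| 176 | 0.5 | 0.830 | 0.731 | 0.909 |
| 216 | 0 | 0.797 | 0.693 | 0.883 |
| 216 | 0.5 | 0.904 | 0.824 | 0.958 |

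**5. Correlation needed to reach 0.80.** White only: about 0.44 at 176 evaluable and 0.09 at 216. Equal weights: about 0.60 at 176 and 0.45 at 216.

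**6. Sensitivity to the race mix.** At 40% non-White, 176 evaluable and rho = 0, power is 0.562 for White only and 0.785 for equal weights.

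**The case against.** **The coding is not given.** Only the group variable is called a dummy; race is called dichotomous. With race centred at its mean, the group term would be the share-weighted effect. The plan's rule for interpreting the interaction coefficient fits either coding. This stands: the White-only reading follows from ordinary 0/1 coding, not from a stated rule.

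**A two-step reading is possible.** The race paragraph opens as an addition to a model already described, and its stated purpose is to look at differential effects. It may describe a later moderation model. Against this, it puts the terms in each regression model, and the main model already includes moderators of interest. The single-model reading is the more natural one, and if two steps were meant the plan should say so.

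**Group x time already calls for a contrast.** Unless 1 month is the reference level, the analyst has to build a 1-month contrast anyway and could set race weights there. That is correct, and it makes the problem wider than race. It does not settle which weights would be used.

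**Power.** A reader might infer that the interaction makes the power claim false or leaves the trial underpowered. The documents do not support that. The share-weighted contrast from the same interaction model keeps 0.803 at 176 evaluable, so the term itself costs essentially nothing. The plan adjusts for baseline, which could restore 80% for the other contrasts, and at 216 evaluable the White-only figure is 0.797 even without that gain. The sample-size text also mentions moderators and lost degrees of freedom, although the 88 per group makes no provision for an interaction.

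**Conclusion.** The point holds as a mis-targeted primary test. Followed as written with the usual coding or the usual Type 3 output, section 13.0 does not test the all-patient half of H1 or H2 at 1 month. The interaction term is not in itself the fault: the all-patient effect can be recovered from the same model once the contrast is specified.

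The lower-bound statement is not demonstrated for contrasts other than the all-patient one, which is weaker than saying it is wrong. With 20% non-White, 176 evaluable and no baseline gain, the shortfall from 0.80 is about 0.10 for White only and 0.21 for equal weights; it disappears at the correlations in step 5. A strong baseline correlation would restore power but would not change which effect is estimated.

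The size of any bias cannot be stated. It is proportional to an interaction for which the documents give no value, and the 0.40 and 0.75 effects are illustrative only. The 20% share is an expectation that refocused recruitment could change.

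**What to change.** In section 13.0, for self-efficacy and for decisional conflict, name the primary test as the mychoice-control difference at 1 month in all randomised patients, obtained in one of two ways:
- from a model without race x treatment, in which race may stay as a main effect; or
- from an ESTIMATE contrast on the interaction model that weights the race-specific effects by the observed race shares.

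State that race x treatment is used only in a separate moderation analysis for each outcome, and give the coding of race and the reference time. Tie the 80% power statement to the named contrast, and either drop the lower-bound sentence or limit it to that contrast.

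The cost is a few sentences and one extra model or one ESTIMATE statement per outcome. No new data and no change in sample size are needed.
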